2.3. Sample Size

Study agreement analyses will be done per joint. To give a kappa ≥ 0.61 (from substantial interrater agreement to almost perfect agreement) with a confidence interval width of 0.15 and the expectation of approximately 20 % of joints assessed having any synovitis in B mode (based on a previous study by our group), 683 joints would be required.⁴ This corresponds to 30 patients if 24 joints per patient are assessed. Non-inferiority margin will be $\kappa \geq 0.61$.

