4.3 Ultrasound Protocol (Assessment of Joints and Enthesis)

Each patient will have consecutive (same day) US examinations using the Clarius handheld and GE gold-standard devices. All scans will be performed in a darkened room. Power Doppler settings will be standardized with a pulse repetition frequency of 500 Hz and low wall filters. The colour gain will be increased to the highest value where power Doppler signals under the bony cortex are not generated. There will be no further training for this step as the 3 investigators have done multiple research projects together and separately, with reproducibility being tested and presented.¹⁵ However, there will be a investigators meeting prior to data collection to review all anatomical sites, positioning and standard views and agree on labelling. All images will be labeled to identify anatomical site and laterality. A glossary will be provided for labelling, to ensure blinding in the later stages. At least one B mode and one power Doppler image will be saved for each site and lesion. The standard will be saving the images in longitudinal views. Transverse views will be saved if there is an abnormality noted on the long axis.

Representative images will be collected and saved for all of the following structures bilaterally:

Joints (24 total): 2nd-3rd metacarpophalangeal (MCP), 2nd-3rd proximal interphalangeal (PIP), 2nd-3rd distal interphalangeal (DIP), wrist, elbow, shoulder, knee, ankle and 5th metatarsophalangeal (MTP) joints of the foot, bilaterally. For the MCP, PIP and DIP joints, if joints other than the 2nd or 3rd present with swelling (e.g. 4th or 5th) they will be scanned instead. This approach is to ensure a maximum number of swollen joints will be assessed.

Entheses (20 total):

Large entheses: Supraspinatus, triceps, common extensor tendon, quadriceps, patellar ligament (origin and insertion), Achilles tendon, Plantar fascia insertions;

Small entheses: extensor digitorum tendon insertion at the DIP and PIP level

Tendons (4 total): Extensor digitorum tendon of the second digits, tibialis posterior tendon in the ankles

Nail: In case of having a nail PsO, the most involved nail and contralateral side will be assessed. If there is no nail PsO, procedure will be performed on the nail of the 2nd digit of the hands.

All study procedures and that will take place in one study visit, as summarize in Table-1.

Table-1: Assessment schedule

Procedures	Visit 1
Obtain informed Consent	x

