Doppler Signal: The presence of positive Doppler signal at the enthesis, confirmed in two perpendicular planes and distinguished from reflection of surface artifacts and nutritional vessel signal.

The intensity of the Doppler signal at the enthesis will be graded using a semi-quantitative score.

Note: we will consider any Doppler signal at the enthesis area including signals appearing beyond 2 mm of the bony cortex, however, not including Doppler signals at the bursa which will be scored separately.

We will score the intensity of the Doppler signal on a semi quantitative grading system:

- **Grade 0:** No Doppler signal
- **Grade 1:** A single confluent Doppler signal or up to 3 discrete Doppler spots
- **Grade 2:** Doppler signal affecting less than half of the enthesis
- **Grade 3:** Doppler signal covering more than half of the enthesis

In addition, the **location of each Doppler signal** will be recorded:

- **Zone 1:** $\leq 2\text{mm}$ from the bone cortex – Zone 1
- **Zone 2:** $>2\text{mm}$ from the bone cortex – Zone 2

4.4 Statistical Analysis:

The primary endpoint analysis will be the interrater agreement of detecting any synovitis in B mode with the Clarius and gold standard machine. The kappa coefficients will be evaluated using the guideline outlined by Landis and Koch, where the strength of the kappa coefficients are: 0.01-0.20 slight; 0.21-0.40 fair; 0.41-0.60 moderate; 0.61-0.80 substantial; 0.81-1.00 almost perfect.¹⁹

For secondary outcomes, the interrater agreement for the presence of Doppler signals within the joints, tenosynovitis, erosions, nail, as well as features of enthesitis (hypoechogenicity, thickening, erosions, enthesophytes, calcifications) will also be evaluated using the same method. The agreement of the semiquantitative grading of the intraarticular findings' severity (synovitis in B mode, Doppler signals, erosions, each being on a scale between 0-3) will be done using weighted kappa analysis.²⁰

An interim analysis will be done after 10 patients. A moderate level of interrater agreement within that sample size (primary outcome) will allow parallel initiation of subsequent studies proposed in the research framework.

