4.5 Sample Size Consideration

Study agreement analyses will be done per joint. To give a kappa ≥ 0.61 (from substantial interrater agreement to almost perfect agreement) with a confidence interval width of 0.15 and the expectation of approximately 20 % of joints assessed having any synovitis in B mode (based on a previous study by our group), 683 joints would be required.¹⁸ This corresponds to 30 patients if 24 joints per patient are assessed. Non-inferiority margin will be $\kappa \geq 0.61$.

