3.1. Confidence Intervals and P-values

We will consider $p < 0.05$ statistically significant for our outcomes. Results will be presented with their values with the 95% confidence interval.

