5.1.2. Secondary Outcomes

5.1.2.1. Joints

After the imaging of all patients is completed, the intraarticular Doppler scoring will be done based on the OMERACT definitions (scales of 0-3) (Table 1):^{5,6}

Power Doppler signal:

Grade 0: no flow in the hypoechoic synovial hyperplasia

Grade 1: up to three single spots signals or up to two confluent spots or one confluent spot plus up to two single spots

Grade 2: vessel signals in less than half of the area of the synovium ($\leq 50\%$)

Grade 3: vessel signals in more than half of the area of the synovium ($> 50\%$)

Also, a lateral view of the 2nd metacarpophalangeal and 5th metatarsophalangeal joints will be recorded in the baseline visit for erosion assessment. Erosions will be described as intra-articular discontinuity of the bony surface seen in 2 perpendicular planes and will be evaluated after the imaging of all patients is completed.

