5.2. Analysis Methods

Demographic, clinical and disease characteristics of patients will be presented using descriptive statistics. Numeric data showing normal distribution will be shared with mean and standard deviation, and those without normal distribution will be shared with median and interquartile range. Categorical data will be shared with numbers and percentages.

The primary endpoint analysis will be the interrater agreement of detecting any synovitis in B mode with the Clarius and gold standard machine. The kappa coefficients will be evaluated using the guideline outlined by Landis and Koch, where the strength of the kappa coefficients are: 0.01-0.20 slight; 0.21-0.40 fair; 0.41-0.60 moderate; 0.61-0.80 substantial; 0.81-1.00 almost perfect.⁷

For secondary outcomes, the interrater agreement for the presence of Doppler signals within the joints, tenosynovitis, erosions, nail, as well as features of enthesitis (hypoechoicity, thickening, erosions, enthesophytes, calcifications) will also be evaluated using the same method. The agreement of the semiquantitative grading of the intraarticular findings' severity (synovitis in B mode, Doppler signals, erosions, each being on a scale between 0-3) will be done using weighted kappa analysis.⁸

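### The 683 joints assume independence but come from 24 joints in each of 30 patients; with no design effect or clustered interval, the 0.15 CI width is not secured

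*SAP*

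**What the plan says.** Protocol 4.5 and SAP 2.3 carry the same text. The unit of analysis is the joint: "Study agreement analyses will be done per joint". For kappa of at least 0.61, an interval width of 0.15 and about 20% of joints with any B-mode synovitis, they require 683 joints. The conversion to patients is one sentence: "This corresponds to 30 patients if 24 joints per patient are assessed". Both sections also call kappa of at least 0.61 a non-inferiority margin, without saying whether the estimate or a confidence limit is compared with it.

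On analysis, SAP 5.2 states: "The primary endpoint analysis will be the interrater agreement of detecting any synovitis in B mode with the Clarius and gold standard machine". Protocol 4.4 adds: "The kappa coefficients will be evaluated using the guideline outlined by Landis and Koch". SAP 3.1 promises intervals: "Results will be presented with their values with the 95% confidence interval". Kappa and weighted kappa are named, but no variance or interval method is. SAP 5.3 drops a site for all probes when an image is missing and does not impute.

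**The concern.** Twenty-four joints in one person, scanned on one day by one operator, are not 24 independent observations. Both the frequency of synovitis and the tendency of the two devices to disagree can vary from patient to patient, for example with acquisition conditions. Central reading in random order does not remove that variation. If it exists, 720 joints carry less information than 720 independent joints, and an ordinary kappa interval is too narrow.

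The width of 0.15 is the only precision stated for the primary endpoint. Two things are at stake: the planned precision is optimistic, and the reported 95% intervals may cover less than 95%. If the 0.61 margin is meant to be judged on a lower limit, the conclusion could change as well. The same problem affects secondary kappas with many sites per patient (joint Doppler, 20 entheses).

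**Working it through.** **Inputs from the plan (SAP 2.3, 3.1):** kappa k = 0.61, prevalence p = 0.20, full width w = 0.15, 95% confidence, 30 patients with 24 joints each. Equal prevalence on both devices is assumed.

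**1. The plan's own figure.** The large-sample variance of kappa per independent joint, for a binary finding with equal marginals, is

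V = (1 − k)[(1 − k)(1 − 2k) + k(2 − k) / (2p(1 − p))].

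At k = 0.61, V = 0.99992. Then n = 4 × 1.959964² × V / 0.15² = 682.87, so 683. The match is exact and leaves no room for an allowance for clustering.

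**2. The reserve.** 30 × 24 = 720 joints, and 720 / 682.87 = 1.054. With design effect 1 + 23 × ICC, this is exhausted at ICC = 0.054 / 23 = 0.0024, before any image is lost. ICC here means the within-patient correlation of the joints' contributions to kappa.

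**3. Width with clustering.** Width = 2q√(V(1 + 23 × ICC) / 720). The planning value q = 1.96 gives 0.146 at kappa 0.61 and ICC 0. With 30 independent patients, q = t(29) = 2.0452 is the suitable multiplier. All ICCs below are assumed.

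| Kappa | V | ICC 0 | 0.01 | 0.02 | 0.05 | 0.10 |
|---|---|---|---|---|---|---|
| 0.61 | 0.99992 | 0.152 | 0.169 | 0.184 | 0.224 | 0.277 |
| 0.70 | 0.81712 | 0.138 | 0.153 | 0.167 | 0.202 | 0.250 |
| 0.80 | 0.57600 | 0.116 | 0.128 | 0.140 | 0.170 | 0.210 |
| 0.90 | 0.30137 | 0.084 | 0.093 | 0.101 | 0.123 | 0.152 |

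The largest ICC that keeps 0.15 is 0.0024, 0.013, 0.036 and 0.109 at kappa 0.61, 0.70, 0.80 and 0.90 with z. With t(29) it is 0.008, 0.030 and 0.096 at the last three, and no ICC of 0 or more keeps it at 0.61.

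**4. Coverage of the ordinary interval.** The simulation used 30 patients × 24 joints, 20% prevalence and 20,000 replicates, with patient-level beta variation in prevalence and in the handheld's sensitivity and specificity against the reference device. These ICCs are on the sensitivity/specificity scale. At kappa 0.61, values of 0.02, 0.05, 0.10 and 0.20 correspond to 0.013, 0.026, 0.048 and 0.096 on the scale of step 3.

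| Setting | Ordinary, kappa 0.61 | Jackknife t(29), 0.61 | Ordinary, 0.80 | Jackknife t(29), 0.80 |
|---|---|---|---|---|
| No clustering | 94.7% | | | |
| Prevalence only, ICC 0.10 | 93.8% | | | |
| Prevalence only, ICC 0.30 | 92.3% | | | |
| Prevalence 0.10 and sens/spec 0.02 | 91.2% | 94.6% | 90.7% | 94.3% |
| Prevalence 0.10 and sens/spec 0.05 | 87.7% | 94.6% | 87.4% | 94.4% |
| Prevalence 0.10 and sens/spec 0.10 | 82.2% | 94.6% | 81.3% | 93.5% |
| Prevalence 0.10 and sens/spec 0.20 | 72.4% | 93.8% | 70.7% | 92.1% |

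The last four rows include prevalence clustering, so not all of the loss comes from disagreement. Without it, coverage at kappa 0.61 is about 93%, 90% and 84% at sens/spec ICC 0.02, 0.05 and 0.10.

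In those four rows at kappa 0.61 the jackknife widths were 0.173, 0.192, 0.220 and 0.268. The formula of step 3 gives 0.174, 0.193, 0.221 and 0.273, so the width table is a fair guide.

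**5. Outcomes with few sites per patient.** At ICC 0.10 the design effect is 1.10 for 2 sites, 1.30 for 4, 2.90 for 20 and 3.30 for 24. Nails and each tendon have about 2 sites ("Tendons (4 total): Extensor digitorum tendon of the second digits, tibialis posterior tendon in the ankles"). Erosions have 4 joints if they are read only where the SAP plans the extra view ("a lateral view of the 2nd metacarpophalangeal and 5th metatarsophalangeal joints will be recorded in the baseline visit for erosion assessment"). Clustering matters little there, and the jackknife becomes unreliable for rare findings: with 2 sites it covered 81% at 5% prevalence and was undefined in 9% of replicates; at 2% prevalence it covered 64% and was undefined in 54%.

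**The case against.** The strongest reply is that no harm is shown. The documents give no ICC, both devices scan the same joint on the same day, and one reader scores everything, so patient-level variation in disagreement is plausible but assumed. Results are read in Landis and Koch bands, the interim gate uses a kappa value and not a limit, and clustering barely moves the estimate. For weighted kappa with a patient-level shift in severity, the ordinary interval still covered 93–95%. All of this stands, and it is why the claim is that the width is not secured, not that it is wrong by a known amount.

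Prevalence may also exceed 20%, since patients need a tender and swollen joint and swollen finger joints are substituted in. At kappa 0.61 the z-based break-even ICC would then be 0.0106 at 25%, 0.017 at 30% and 0.026 at 40%; at 15% it is below zero. The reserve stays small throughout.

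On the other side, the undefined use of the 0.61 margin could raise the importance. An observed kappa of 0.70 has a lower limit (z) of 0.634 with independent joints, 0.603 at ICC 0.05 and 0.580 at ICC 0.10.

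Finally, the jackknife is one valid method among several; a patient-level bootstrap or a cluster-robust variance would also serve. The width table holds only for 24 joints pooled over the two probes. Separate kappas for the L15 (12 joints) and L20 (16 joints) would have independent-joint widths of about 0.207 and 0.179 at kappa 0.61.

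**Conclusion.** The concern holds and should be fixed. That 683 is the independent-joint answer, and that neither document allows for clustering in the size or in the interval, is certain. The size of the loss is not: it is small if only prevalence clusters and material if device disagreement varies between patients. Under-coverage is not confined to kappa 0.61; it is as large at 0.80. These figures rest on 20% prevalence, equal marginals, complete images and assumed ICCs. The harm is to stated and reported precision, and reaches the conclusion only if a confidence limit is to be compared with 0.61.

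**What to change.** 1. **SAP 3.1 and 5.2:** prespecify a patient-level jackknife for the 95% interval, with t on the number of contributing patients minus 1 (29 at the final analysis). Apply it to the primary kappa and to the joint and enthesis kappas and weighted kappas with many sites per patient. Another patient-clustered method is acceptable if named in advance.
2. **Nails, tendons and erosions:** do not require the jackknife; name the interval that will be used. For these and for rare enthesis lesions, report raw agreement and the 2×2 counts beside kappa. With 20 entheses the jackknife covered 93–95% at 5–20% prevalence but 90–94% at 2%.
3. **SAP 2.3 and Protocol 4.5:** say that 0.15 assumes independent joints and all 24 joints pooled across the two probes, and give the width table above for 30 patients. Say also whether the 0.61 margin applies to the estimate or to a limit.

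The cost is wording and a few lines of code, a less favourable stated precision, and a slightly wider interval even without clustering (0.152 against 0.146 at kappa 0.61). No extra patients are needed for this. Holding 0.15 at kappa 0.61 is a different matter: on the planning formula it would take 35, 42, 62 or 94 patients at ICC 0.01, 0.02, 0.05 or 0.10.

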2.4. Statistical Interim analyses and stopping guidance

An interim analysis will be done after 10 patients. In the interim analysis, the agreement between the images obtained with the handheld ultrasound and the images on the gold standard device will be compared after the blinded scoring. A moderate level of agreement (defined as a kappa value of >0.40) between the two tools in the interim analysis will allow parallel initiation of subsequent studies proposed in the research framework. The results of this interim analysis will not be used to adjust the design of the remainder of the study. We do not have any formal stopping rules for the trial.

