5.1. Outcome Definition

5.1.1. Primary Outcome

After the imaging of all patients is completed, intraarticular synovitis scoring will be done based on the OMERACT definitions (scales of 0-3) as follows, for the anatomical sites given in Table 1.^{5,6}

Greyscale inflammatory (hypoechoic) synovial hyperplasia:

Grade 0: no hypoechoic synovial hyperplasia

Grade 1: minimal hypoechoic synovial hyperplasia (filling the angle between the periarticular bones, without bulging over the line linking tops of the bones)

Grade 2: hypoechoic synovial hyperplasia bulging over the line linking tops of the periarticular bones but without extension along the bone diaphysis

Grade 3: hypoechoic synovial hyperplasia bulging over the line linking tops of the periarticular bones and with extension to at least one of the bone diaphysis

Table-1:Probes/scanners, views and anatomical sites for primary outcomes

Anatomical site	Views	GE Logic E9/S8	Clarius L15	Clarius L20
2nd MCP joints	dorsal and lateral	X	X	X
3rd MCP joints	dorsal	X		X
2nd-3rd PIP, 2nd-3rd DIP	dorsal	X		X
Wrist	dorsal	X	X	X
5th MTP joints	dorsal and lateral	X		X
Elbow joints	posterior	X	X	
Shoulder joints	posterior	X	X	
Knee joints	anterosuperior	X	X	
Ankle joints	anterior	X	X	

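### The non-inferiority margin of kappa 0.61 has no decision rule: the plan does not say whether the estimate or its lower confidence limit must reach it

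*SAP*

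**What the plan says.** The margin appears once in each document, inside the sample size section. SAP 2.3 reads "Non-inferiority margin will be $\kappa \geq 0.61", and Protocol 4.5 has the same sentence. The calculation beside it is about precision: "To give a kappa ≥ 0.61 (from substantial interrater agreement to almost perfect agreement) with a confidence interval width of 0.15". It expects about 20% of joints to show B-mode synovitis and arrives at 683 joints, or 30 patients with 24 joints each.

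The analysis sections do not return to the margin. SAP 5.2, with the same text in Protocol 4.4, says "The primary endpoint analysis will be the interrater agreement of detecting any synovitis in B mode with the Clarius and gold standard machine" and then interprets the coefficient by the Landis and Koch bands: "0.41-0.60 moderate; 0.61-0.80 substantial; 0.81-1.00 almost perfect". The value 0.61 is the bottom of the substantial band.

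SAP 3.1 says "Results will be presented with their values with the 95% confidence interval" and sets significance at p < 0.05. It names no null value of kappa and gives the interval no role against 0.61. The only other threshold is the interim one in SAP 2.4, again a bare value: "A moderate level of agreement (defined as a kappa value of >0.40) between the two tools in the interim analysis".

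**The concern.** A non-inferiority claim normally means that values worse than the margin have been excluded at a stated confidence level. Here the margin is named, but the step from data to claim is missing. Two analysts could follow the same plan, observe a kappa of 0.65 and reach opposite conclusions. One would say that 0.65 exceeds 0.61 and falls in the substantial band. The other would say that the interval includes moderate agreement. With nothing fixed in advance, the choice could be made after the data are seen.

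The documents describe the study as the validation needed before the handheld devices are used in rheumatology, so how the primary kappa supports that statement matters.

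It is also open which kappa would be compared with 0.61. SAP 5.2 speaks of a single Clarius device, whereas the SAP table headed "Table-1:Probes/scanners, views and anatomical sites for primary outcomes" lists two handheld scanners, with the 2nd MCP joints and the wrists scanned by both.

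**Working it through.** **Inputs.** From SAP 2.3: kappa k = 0.61, full interval width 0.15, prevalence p = 0.20, and 30 × 24 = 720 joints. From SAP 3.1: 95% confidence, z = 1.96. The documents give no true kappa, no power and no within-patient correlation, so values used for these below are assumptions.

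**1. Reproduce the 683.** The large-sample variance of kappa for a binary rating with equal margins is

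n·Var = (1 − k)[(1 − k)(1 − 2k) + k(2 − k) / (2p(1 − p))].

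With k = 0.61 and p = 0.20:

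- (1 − k)(1 − 2k) = 0.39 × (−0.22) = −0.0858
- k(2 − k) / (2p(1 − p)) = 0.8479 / 0.32 = 2.6497
- n·Var = 0.39 × 2.5639 = 0.9999

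N = 4z² × 0.9999 / 0.15² = 682.9, rounded up to 683. This matches the plan exactly. A half-width of 0.15 would give 171 and a 90% interval 481, so the plan means a full width of 0.15 at 95%. An interval of that width centred on 0.61 has its lower limit near 0.535 by design.

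**2. Interval at an observed 0.61.** With 720 joints the standard error is √(0.9999/720) = 0.0373 and the half-width 0.073, giving 0.537 to 0.683. With 683 joints it is 0.535 to 0.685. At 720 joints, a prevalence of 10% gives 0.512 to 0.708 and 30% gives 0.547 to 0.673.

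**3. Where the two readings part.** With 720 joints the lower limit is 0.591 at an observed 0.66 and 0.601 at 0.67. It reaches 0.61 at 0.678. Between 0.61 and just under 0.68, comparing the estimate and comparing the lower limit therefore give different answers. Up to about 0.67 the interval also reaches the moderate band, which ends at 0.60.

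**4. Chance of meeting each rule (720 independent joints, p = 0.20).**

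| True kappa | Estimate ≥ 0.61 | Lower limit ≥ 0.61 |
|---|---|---|
| 0.55 | 6% | <1% |
| 0.58 | 22% | <1% |
| 0.60 | 40% | 2% |
| 0.65 | 87% | 22% |
| 0.70 | >99% | 74% |
| 0.75 | >99% | 99% |

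Under the lower-limit rule, 80% power needs a true kappa of about 0.71.

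**5. Clustering (assumed ICC).** The design effect for 24 joints per patient is 1 + 23 × ICC.

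| ICC | Design effect | Interval at 0.61 | Observed kappa needed | Power at true 0.70 | True kappa for 80% power |
|---|---|---|---|---|---|
| 0.05 | 2.15 | 0.503 to 0.717 | 0.706 | 45% | 0.74 |
| 0.10 | 3.30 | 0.477 to 0.743 | 0.726 | 34% | 0.77 |

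**6. Per scanner.** SAP Table 1 gives 16 joints per patient for the L20 (2nd MCP 2, 3rd MCP 2, PIP 4, DIP 4, wrist 2, 5th MTP 2) and 12 for the L15 (2nd MCP 2, wrist 2, and 2 each for elbow, shoulder, knee and ankle). Over 30 patients that is 480 and 360. With joints independent, the intervals at 0.61 are 0.521 to 0.699 and 0.507 to 0.713.

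**The case against.** The strongest reply is that no sentence says an observed 0.61 is enough. Comparing a confidence limit with a margin is the usual meaning of non-inferiority, and SAP 3.1 commits to 95% intervals, so a reader would see 0.54 to 0.68 beside the 0.61. This stands in part. A reader might infer that the plan has adopted a point-estimate rule; the documents do not say so, and the pass rates for that rule apply only if it is the one used. The bands and the interim threshold make it plausible but do not settle it. The interim threshold in particular only lets other studies start. What the reply does not supply is the missing rule: showing an interval does not say what it must exclude.

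A second reply is that non-inferiority is one sentence in a sample size section, while the primary analysis is a graded kappa. That bears on weight. It also supports deleting the sentence if estimation is all that was intended.

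A third is that the choice of scanner and within-patient clustering are separate questions. They are: the gap would exist with one scanner and independent joints. They enter here only because a rule cannot be written without naming the kappa and its interval. The clustering figures rest on an assumed ICC.

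**Conclusion.** The concern holds as a missing decision rule and should be fixed. The 683 is arithmetically right, and the interval will be reported; the defect lies in neither. The consequence is a range of observed kappa, from 0.61 to just under 0.68, in which the claim depends on an unwritten choice. That range assumes 720 independent joints and 20% prevalence. Clustering within patients or analysis per scanner would widen it. It would be too strong to say that the plan accepts an observed 0.61 as proof of non-inferiority: that is the most natural reading, not a stated rule. It would equally be unsafe to assume the lower-limit rule, since the sample size was not built for it.

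**What to change.** Choose one of the following.

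1. **Estimation only.** Delete the non-inferiority sentence from SAP 2.3 and Protocol 4.5. Report the primary kappa with a 95% interval from a bootstrap that resamples patients. This matches the precision-based sizing. The cost is the loss of the non-inferiority label.

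2. **A stated rule.** Write in SAP 5.2 and Protocol 4.4: *The claim of at least substantial agreement requires the lower limit of the two-sided 95% confidence interval for the primary kappa, from a bootstrap resampling patients, to be at least 0.61. The Landis and Koch bands are descriptive only.* Then:
   - Name the primary kappa. If pooled over 24 joints, say which handheld supplies the 2nd MCP and wrist readings. If per scanner, say whether both must pass.
   - State in SAP 2.3 and Protocol 4.5 that the study was not sized for this rule. With 720 independent joints, 80% power needs a true kappa of about 0.71; under an assumed ICC of 0.05 to 0.10 it needs about 0.74 to 0.77.

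   The cost is that the claim becomes harder to make.

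Either way the work is a few sentences in the two documents and a patient-level bootstrap in the analysis code, plus the choice of primary kappa under option 2. No patients or images are added.
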